#### 4.4EXCLUSION CRITERIA

The following are exclusion criteria for subjects in this study:

- 1. Pregnancy, currently breast feeding or planning pregnancy for the duration of the trial
- 2. Any UNCONTROLLED systemic disease -a potential patient in whom therapy for a systemic disease is not yet stabilized will not be considered for entry into the study
- 3. Treatment with botulinum toxin injections in the neck or chin area within 6 months before randomization
- 4. Any Scars, unshaven hair, tattoos or jewelry on or near the proposed treatment area
- 5. Significant history or current evidence of a medical, psychological or other disorder that, in the investigator's opinion, would preclude enrollment into the study
- 6. An active dermatitis or open wound in the proposed treatment area
- 7. An active bacterial, fungal, or viral infection in the proposed treatment area
- 8. Pre-existing skin condition to the submental region that may confound evaluation or analysis, at investigator discretion
- 9. Previously treated with subcutaneous sodium deoxycholate to the submental region
- 10. Previously treated with focused ultrasound, radiofrequency, cryolipolysis or liposuction to the submental region within the previous 6 months
- 11. Any other laser, light energy device, or chemical peel treatment to the submental region within the previous 3 months
- 12. Pre-existing neurological or gastrointestinal condition leading to dysphagia, dysphonia or facial nerve palsy

- 13. Pre-existing medical condition other than increased submental fat that may result in increased submental fullness such as but not limited to thyroid enlargement, goiter, cervical lymphadenopathy etc., at investigator discretion
- 14. Must not have a planned fat reduction procedure of any variety to the submental region for the duration of the study
- 15. Must not have planned significant alterations in diet or physical activity that may result in significant fluctuations in weight
- 16. Current participation or participation within 30 days prior to the start of this study in a drug or other investigational research study.

# 5. MATERIALS AND METHODS

#### 5.1 Washout Period

- A patient must not have been previously treated with focused ultrasound, radiofrequency, cryolipolysis or liposuction to the submental region within the previous 6 months.
- The patient must not have had any other laser, light, energy device, or chemical peel treatment to the submental region within the previous 3 months.
- The patient must not have participated in a drug or other investigational research study involving the proposed treatment area within 30 days prior to the start of this study.

# 6. STUDY PERIOD

# Visit 1 (Day 1, Baseline)

- Obtain written Informed Consent and HIPPA
- Record Medical History and Concomitant Medication
- Review Inclusion and Exclusion
- Record Subjects weight
- Randomization
- Pregnancy Test (If applicable)
- Photographs
- Blinded-Investigator Grade (CR-SMFRS) and (SMSLG)
- Treatment #1 with either Kybella(TM) alone or varying doses of TMC

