# 4.2 Study Endpoints

# a. Investigator Evaluations (Appendix A)

- The Clinician-Reported Submental Fat Rating Scale will be completed by a blinded-investigator on Visit Days 1, 30, 60, 90 and 180.
- The Submental Skin Laxity Grade (SMSLG) will be completed by a blinded-investigator on Visit Days 1, 30, 60, 90, and 180.
- A Side Effects Scale will be completed by a blinded-investigator at all follow-up visits. The side effects evaluated will include Edema, Erythema, Tenderness, Erosion/Ulceration, Steroid Atrophy, Induration, and Marginal Mandibular Palsy.

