# b. Subject Evaluations (Appendix B)

- The Subject Evaluation of Side Effects Scale will be completed at Visits 2 through 11.
- The Subject Satisfaction Rating Scale will be completed by the patient on Visit Day 180.

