# 13. Adverse Events and Reporting

Serious and/or Adverse Event and Reporting

A *serious adverse event* is any untoward medical occurrence, that, at any dose:

- Results in death;
- is life-threatening;
- requires in-subject hospitalization or prolongation of existing hospitalization;
- Results in persistent or significant disability/incapacity;
- is a congenital anomaly/birth defect; or
- is an important medical event.

An *unexpected adverse event* is any treatment-related adverse event, which is not identified in nature, severity, or frequency in current literature on the test product.

Any serious adverse event occurring in this study must be reported to the IRB within 24 hours of awareness of the event. Initial reports must be made by telephone, followed by the completion of a Serious Adverse Event Report and submission by facsimile.

Throughout the study, subjects will be monitored for signs and symptoms of adverse events. An *adverse event* is any pathological or unintended change in the structure, function or chemistry of the body that occurs during the study, irrespective of causality, including any illness, injury, toxicity, sensitivity, or sudden death. The condition must either not be present pre-study or must worsen in either intensity or frequency during the study.

All adverse events, including serious and treatment related or unexpected adverse events, must be recorded by the Investigator. In the event of an adverse event or serious adverse event, the physician will provide optimal patient care.

Subjects who have had a serious adverse event must be followed clinically until all parameters have either returned to normal or are otherwise explained. If death was the outcome of the event on the initial SAE Report, a Follow-up/Final Report, including autopsy report, when performed, must be completed.

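### No pre-treatment score is scheduled on either side-effect scale, so low-grade signs present at entry cannot be subtracted or adjusted for

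*Combined protocol and SAP*

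**What the plan says.** In Section 6, Visit 1 comprises consent, history, eligibility review, weight, randomization, pregnancy test, photographs, the line "Blinded-Investigator Grade (CR-SMFRS) and (SMSLG"), and Treatment #1. Neither side-effect scale is listed.

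Section 4.2 agrees. For the clinician form: "A Side Effects Scale will be completed by a blinded-investigator at all follow-up visits". For the subject form: "The Subject Evaluation of Side Effects Scale will be completed at Visits 2 through 11". Section 14 repeats the follow-up timing. The first scores are therefore taken at Visit 2 (Day 3, plus or minus one day).

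The clinician form covers "Edema, Erythema, Tenderness, Erosion/Ulceration, Steroid Atrophy, Induration, and Marginal Mandibular Palsy". Appendix A grades these from 0 to 4, except palsy, which is present or absent. Section 13 adds, for an adverse event: "The condition must either not be present pre-study or must worsen in either intensity or frequency during the study".

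**The concern.** Several clinician items describe signs that a person can have before any injection. Entry is open to ages 18 to 65 and all six Fitzpatrick skin types. Grade 1 atrophy and grade 1 induration are defined as barely perceptible, and palsy has no gradation at all. A sign of that size seen on Day 3 or Day 180 has no entry grade to be compared with.

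Atrophy matters most. Section 1 reports it in 7 of 15 triamcinolone subjects (47%) in the earlier study and gives its avoidance as one reason for trying a lower concentration. An atrophy count that includes pre-existing thin skin would blur the result on that point.

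Visits 4 and 7 list both scales ahead of the injection, but those grades follow one and two earlier treatments. No treatment-naive grade exists.

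**Working it through.** **1. Schedule.** The plan states no figure to reproduce here. Counting from Sections 4.2 and 6, there are 0 scheduled pre-treatment scores for the 7 clinician items and 0 for the 5 subject items.

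**2. What other entry information exists.**

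| Source at Visit 1 | What it gives | What it lacks |
|---|---|---|
| Medical history, eligibility review | Known conditions, investigator judgement | A grade on any item |
| SMSLG (Appendix A) | Examination with palpation | Separate items: wrinkling, adherence and redundancy become one whole number |
| Photographs (Appendix C) | Standardized pre-treatment image | A grade; tenderness, induration or movement, which a still image cannot show |

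Section 3 places Vectra imaging at baseline and final visit with a different system at other visits, while Appendix C places Vectra at all visits. Whether an early follow-up photograph matches the baseline one therefore depends on which text is followed.

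**3. Size, on an assumed prevalence.** Section 3 gives 5 and 10 subjects per arm at each of two sites, so 10 controls and 20 triamcinolone subjects, 30 in all. Let p be the share of entrants with a given sign, the same in both arms because allocation is random. The documents give no value, so p is varied.

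- Expected carriers: 10p and 20p.
- At least one carrier among 30: 1 − (1 − p)^30.
- Chance imbalance: P(|A/10 − B/20| ≥ 0.20), with A binomial(10, p) and B binomial(20, p), summed exactly.

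| p (assumed) | Carriers, control vs triamcinolone | At least one of 30 | Imbalance of 20 points or more |
|---|---|---|---|
| 5% | 0.5 vs 1 | 79% | 5% |
| 10% | 1 vs 2 | 96% | 13% |
| 20% | 2 vs 4 | over 99% | 26% |

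If no subject developed new atrophy, the recorded incidence in each arm would still be about p if every carrier were scored. That figure would then be read against 7/15 = 47%. For mean scores, one subject with a pre-existing grade 2 shifts the control mean by 2/10 = 0.2 or the triamcinolone mean by 2/20 = 0.1.

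**4. What a baseline covariate could gain.** Section 14 sets significance at 0.05 without stating sidedness; two-sided is assumed, with 80% power and a normal approximation. The detectable difference in SD units is (1.9600 + 0.8416) × √(1/10 + 1/20) × √(1 − ρ²), where ρ is the assumed correlation between baseline and follow-up score.

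| ρ (assumed) | Detectable difference |
|---|---|
| 0 | 1.09 SD |
| 0.3 | 1.04 SD |
| 0.5 | 0.94 SD |
| 0.7 | 0.77 SD |

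An item that is zero in nearly everyone at entry gains essentially nothing.

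**The case against.** **Randomization and the concurrent control.** Pre-existing signs are expected equally in both arms, so the expected difference between arms from this source is zero. This stands. A reader might infer that the triamcinolone arm would be systematically charged with false cases; the design does not support that.

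**Eligibility.** A reader might infer that Exclusions 8 and 12 cannot be applied without the scale. They can. Exclusion 8 reads "Pre-existing skin condition to the submental region that may confound evaluation or analysis, at investigator discretion", and Exclusion 12 concerns a pre-existing neurological or gastrointestinal condition, which is a matter of history. Visit 1 schedules "Record Medical History and Concomitant Medication" and "Review Inclusion and Exclusion" ahead of Treatment #1, and neither exclusion refers to a score.

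**Adverse events.** Section 13 asks for pre-study status, not a 0 to 4 grade, and adverse events are reviewed separately from the scales at each follow-up visit. It would be too strong to say that treatment effects and prior conditions cannot be told apart: history, photographs and the SMSLG examination give partial evidence. What remains is that none of these yields an entry grade, which is the natural starting point for judging worsening in intensity.

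**Screening and rater judgement.** Exclusions 4, 6, 7 and 11 (scars, dermatitis or wounds, infection, recent laser or peel) remove many sources of redness or erosion, and the form asks for treatment side effects, so a rater may discount long-standing features. Both points lower the plausible p. But mild signs not judged confounding can still enter, and discounting without a recorded grade rests on memory and may differ between the two sites.

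**The named outcomes.** The objective in Section 2 names edema and pain. Swelling, pain and bruising should be near zero before injection, so the gap matters little for them. This also stands.

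**Conclusion.** The gap is real and confined to low-grade erythema, atrophy, induration and facial asymmetry. It affects individual attribution, absolute incidence and chance imbalance; it does not bias the randomized comparison in expectation, and no figure in the plan changes. For an assumed prevalence of 5% to 20% in both arms, the chance of an imbalance of 20 points or more is 5% to 26%. The prevalence and the baseline correlation are assumptions without support in the documents, and the exclusions argue for the lower part of the prevalence range. The importance is minor to moderate, but the change is cheap and cannot be made after the first injection.

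**What to change.** In Section 6 (Visit 1) and Section 4.2, add the Clinician Side Effects Scale before Treatment #1, completed by the blinded investigator who already grades CR-SMFRS and SMSLG, and preferably by the same rater at follow-up. In Section 14, state that side effects will be reported as new or worsened from that grade, which matches Section 13, with the raw grades also shown. The Subject scale at Visit 1 is optional and of lower value: it has no redness, atrophy, induration or palsy item.

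The cost is one short form at a visit the rater already attends, one added line each in Sections 4.2 and 6, and the reporting sentence in Section 14. No new staff or procedure is needed. Visit 1 lists randomization before the blinded grading; that order can stay, because the grader is blinded and the grade still precedes the injection.

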#### Visit 2 (Day 3 [+/- 1 day])

- Photographs
- Blinded-Investigator Evaluation of Treatment Side Effects
- Subject Evaluation of Side Effects Scale
- Review Con Meds
- Review Adverse Events

# Visit 3 (Day 5 [+/- 1 day])

- Photographs
- Blinded-Investigator Evaluation of Treatment Side Effects
- Subject Evaluation of Side Effects Scale
- Review Con Meds
- Review Adverse Events

# Visit 4 (Day 30 [+/- 3 days])

- Pregnancy Test (If applicable)
- Photographs
- Blinded-Investigator Evaluation of Treatment Side Effects, CR-SMFRS and SMSLG
- Subject Evaluation of Side Effects Scale
- Treatment #2 with either Kybella(TM) alone or varying doses of TMC
- Review Con Meds
- Review Adverse Events

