A previous study was performed using high doses of a corticosteroid. This double-blind, randomized study utilized triamcinolone acetonide (TMC), a corticosteroid compound, in conjunction with Kybella(TM) showed that the addition of TMC reduced the incidence of early edema and tenderness, but negatively impacted long term efficacy and produced cutaneous changes of steroid atrophy in 7 (47%) of the 15 patients treated with TMC [4]. In the study, 2.0 mL of 2 mg/cm2 of Kybella(TM) was mixed with 0.05 mL of 40 mg/mL of TMC, and was delivered in up to 50 injections spaced 1.0 cm apart at 0.25 mL/injection for a total dose of up to 100 mg of Kybella(TM). As the tolerability of Kybella(TM) remains a significant issue in patient care, perhaps lower concentrations of TMC would be effective in reducing side effects without compromising treatment efficacy and causing steroid atrophy.

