#### Visit 7 (Day 60[+/- 3 days])

- Pregnancy Test (If applicable)
- Photographs
- Blinded-Investigator Evaluation of Treatment Side Effects, CR-SMFRS and SMSLG
- Subject Evaluation of Side Effects Scale
- Treatment #3 with either Kybella(TM) alone or varying doses of TMC
- Review Con Meds
- Review Adverse Events

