# B. Subject Discontinuation

**Each subject may voluntarily discontinue** the study at any time they choose. Subjects who cannot complete the study for administrative reasons (e.g., non-compliance, failure to meet visit schedule, etc.) will be discontinued from the study. These patients will be asked to return for completion of visit 11.

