#### C. Subject Termination

A study subject will be terminated if the subject develops signs or symptoms of moderate to severe irritation or any severe adverse event that may be related to the study protocol. A subject will receive appropriate treatment at the discretion of the investigator and will be terminated

from using the treatment regimen. Notification of termination will be clearly documented on the appropriate Case Report Form. These subjects are considered to have completed the study and will not be replaced.

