# **Clinician Evaluation of Side Effects Scale**

	Edema	Erythema	Tenderness	Erosion/ Ulceration	Steroid Atrophy	Induration	Marginal Mandibular Palsy
0	None	None	No tenderness	No erosion/ulcera tion	None	None	Not Present
1	Very slight (barely perceptible)	Very slight	Very slight	Very slight (barely perceptible)	Very slight (barely perceptible)	Very slight (barely perceptible)	Present
2	Slight	Well- defined	Slight	Slight	Slight	Slight	
3	Moderate (raised approximately 1mm)	Moderate to severe	Moderate	Moderate	Moderate	Moderate	
4	Severe (raised more than 1mm and exceeding beyond area of exposure)	Severe (beet red to slight eschar formation)	Severe	Severe	Severe	Severe	

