# Please ensure the following for consistent before and after photos:

- 1. Subjects removal of makeup and face washed at least 20 minutes prior to having their photograph taken to ensure makeup, lotions and/or sunscreens will not interfere with any evaluations (Males must be clean shaven).
- 2. Please ensure that subjects jewelry is removed from ears/neck and hair is pushed back away from the face with a black headband (any stray hairs will cause the VECTRA system to crop the face). A black drape will be placed around the subjects neck to ensure photo consistency. One (1) photo will be taken with eyes closed one (1) image will allow us to capture (5) views (frontal, left oblique, right oblique, left profile and right profile views). The camera we will be using is a Canfield VECTRA. Photos will be captured at ALL visits (on treatment visits day 1, 30 and 60 photos will be captured pre-treatment).

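### Minor: Visits 4 and 7 re-inject whatever that day's side-effect grades show, and the termination rule misses slight steroid atrophy and a non-severe palsy

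*Combined protocol and SAP*

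**What the plan says.** Section 6 lists the tasks for each visit. At Visit 4 (Day 30) the blinded investigator grades side effects, and the list includes "Treatment #2 with either Kybella(TM) alone or varying doses of TMC". Visit 7 (Day 60) has the same grading and "Treatment #3 with either Kybella(TM) alone or varying doses of TMC". Nothing at either visit, or elsewhere, says what a grade means for that day's injection.

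Section 4.2 and Appendix A include steroid atrophy and marginal mandibular palsy among the seven clinician-graded side effects. Atrophy runs from 0 to 4, where 2 is slight, 3 moderate and 4 severe. Palsy is coded only as absent (0) or present (1).

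Section 6.4 C terminates a subject who develops "signs or symptoms of moderate to severe irritation or any severe adverse event that may be related to the study protocol". There are other subject-level exits. Section 6.4 B covers voluntary and administrative discontinuation and adds: "These patients will be asked to return for completion of visit 11". Section 7.2 covers pregnancy. Section 6.4 D lets the investigator stop the whole study.

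Two tasks are stated to come before treatment: a negative pregnancy test where applicable (Section 4.3, item 6) and the photographs (Appendix C: "on treatment visits day 1, 30 and 60 photos will be captured pre-treatment").

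Section 1 reports that adding triamcinolone (TMC) in the earlier study "produced cutaneous changes of steroid atrophy in 7 (47%) of the 15 patients treated with TMC".

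**The concern.** The protocol collects atrophy and palsy grades on the same days that it gives the second and third injections, but attaches no action to them. Section 3 separates the roles: the evaluator is blinded and the injector is not. Nothing says that the evaluator's grade reaches the injector before the needle does.

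The stake is subject safety in an elective cosmetic treatment. A subject with visible atrophy could receive more steroid at the same site, and a subject with a nerve palsy could receive more deoxycholate there. With no written rule, the two sites could also treat the same grade differently and both be within protocol.

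**Working it through.** **Step 1. Set the side-effect scale against the termination rule.** Section 13 defines an adverse event broadly enough to include atrophy and palsy, so a severe and possibly related case of either falls under Section 6.4 C.

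| Finding at Visit 4 or 7 | Reached by Section 6.4 C? | Injection that day, as written |
|---|---|---|
| Atrophy grade 1 (barely perceptible) | No | Given |
| Atrophy grade 2 (slight) | No, below moderate | Given |
| Atrophy grade 3 (moderate) | Unclear; turns on whether atrophy is irritation | Unclear |
| Atrophy grade 4 (severe) | Probably, as a severe related event | Stopped, if so |
| Palsy present, not judged severe | No | Given |
| Palsy judged severe and possibly related | Yes | Stopped |

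Irritation is not defined. Section 1 speaks of an irritant mechanism when it discusses edema and pain, which suggests a local reaction rather than atrophy, but that is inference.

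**Step 2. Look for another rule that fills the gap.** The exits in Sections 6.4 B and 7.2 are not linked to side-effect grades, and Section 6.4 D acts on the whole study. Section 13 requires recording, reporting and proper care, but no treatment hold. No text describes omitting one session and continuing.

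**Step 3. Exposure still to come.** Section 3 plans 3 sessions of up to 50 points at 0.2 mL. For the Group 2 mix:

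- TMC: 0.2 mL × 10 mg/mL = 2 mg
- Volume: 2.0 + 0.2 + 0.2 = 2.4 mL, so 2/2.4 = 0.833 mg/mL
- Per point: 0.833 × 0.2 = 0.167 mg
- Per session, at most: 0.167 × 50 = 8.3 mg

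A finding at Day 60 leaves one session (at most 8.3 mg). A finding at Day 30 leaves two (at most 16.7 mg).

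**Step 4. Is the earlier atrophy finding relevant to this dose?** The stated rate reproduces: 7/15 = 46.7%, given as 47%. In the earlier study, Kybella (2.0 mL) was "mixed with 0.05 mL of 40 mg/mL of TMC, and was delivered in up to 50 injections spaced 1.0 cm apart at 0.25 mL/injection".

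- TMC: 0.05 × 40 = 2 mg in 2.05 mL = 0.976 mg/mL
- By injection volume: 0.976 × 0.25 = 0.244 mg per point. This implies 20/2.05 × 0.25 × 50 = 122 mg of deoxycholate, above the stated 100 mg maximum, so a second reading is needed.
- By the 100 mg maximum: 100/50 = 2 mg of deoxycholate per point. The mix holds 2 mg TMC to 20 mg deoxycholate, so 0.20 mg TMC per point.

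Both readings assume Kybella at 10 mg/mL in the earlier study, as Section 3 implies for this one. The planned dose per point is then 0.167/0.244 = 68% to 0.167/0.20 = 83% of the earlier one. If the 1.0 mg/mL label in Section 3 is the final concentration, the planned dose is 0.20 mg per point, or 82% to 100%. The doses are similar enough for atrophy to be foreseeable. The gap found in Steps 1 and 2 is the same on every reading.

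**Step 5. What cannot be computed.** The documents do not give the timing, grade or course of the seven atrophy cases, any palsy frequency, or an atrophy rate at the planned dose. No probability of a finding by Day 30 or Day 60 can be given.

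**The case against.** The strongest reply is that a competent clinician would not inject into an evident palsy or atrophy. Section 13 obliges the physician to give proper care, and adverse events are reviewed at every follow-up visit. The words of Section 6.4 C match grades 3 and 4 of the scale, so only slight atrophy and a non-severe palsy remain. No frequency is known, and a grade 2 cut-off appears nowhere in the documents.

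Much of this stands. Judgement may well prevent harm, the gap is narrow, and the cut-off is a proposal. But judgement is not a written rule, and following the schedule exactly leads to re-injection. The grading is listed before the injection at both visits, but list order does not establish sequence: adverse-event review is listed after it.

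A reader might infer more than the documents support:

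- That Section 6.4 C is the only way a subject can leave. It is the only exit based on side effects; Sections 6.4 B and 7.2 are others.
- That photographs are the only task fixed before treatment. The pregnancy test is too.
- That Sections 6.4 C and 13 disagree about who decides on re-injection. Both concern care of an affected subject; neither assigns that decision.
- That any atrophy should stop dosing. Grade 1 is also outside the termination rule, but it is barely perceptible, and the fix below does not hold treatment for it.

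**Conclusion.** The point holds as a minor, cheap safety improvement. Treatments #2 and #3 are not conditional on that day's grades, no omitted session is provided for, and the one side-effect-based rule misses grade 2 atrophy and a palsy not judged severe. Grade 3 atrophy is ambiguous.

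The size is bounded only by exposure: at most two further sessions after a Day 30 finding and one after a Day 60 finding. The milligram figures assume the stated mix and 50 points. The number of subjects affected is unknown.

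A reader might go on to infer that the gap biases the fat-reduction result. The documents give no basis for that, and it is not claimed.

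**What to change.** At Visits 4 and 7:

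- Complete the blinded side-effect grading and the adverse-event review before injection, and pass the result to the injector.
- Omit that session if palsy is present or atrophy is grade 2 or higher, in both arms and at both sites. The sponsor may choose a stricter cut-off.
- Omit rather than delay, so that the visit windows stand, and re-check at the next treatment visit.
- Let Section 6.4 C take precedence where it applies. Otherwise an omitted session is not a termination: the subject stays in follow-up to Day 180 and is analysed as randomised.
- Report sessions received by arm. Flag side-effect scores at Visits 5 to 7 after an omission at Visit 4, and at Visits 8 to 10 after an omission at Visit 7, because no new injection preceded them.

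The cost is one paragraph in an amendment and one treat-or-omit line on two visit forms, using grades already collected. No visits are added, and sample size and significance level are unchanged.

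There is a downside. Omissions will fall mainly on the TMC arm, slightly reduce its exposure, and may hint at allocation. They also tend to lower swelling and pain scores at the visits that follow, which is why those scores are flagged.
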